5.2. Exclusion Criteria

Participants are excluded from the study if any of the following criteria applies:

Medical conditions

14. Have known or suspected Richter's transformation to diffuse large B-cell lymphoma, prolymphocytic leukemia, or Hodgkin's lymphoma at any time before randomization.
15. Have known or suspected history of central nervous system involvement by CLL/SLL.
16. Previous or concurrent cancer distinct from CLL/SLL within 3 years before randomization. Exceptions may occur with documented sponsor approval. Examples include
 - nonmelanoma skin cancer or lentigo maligna melanoma
 - cervical carcinoma in situ
 - localized prostate cancer undergoing active surveillance, and
 - localized (for example, lymph node negative) breast cancer with no evidence of active disease present for more than 3 years. Individual may be receiving adjuvant hormonal therapy.

17. Have a history of \geq Grade 3 bleeding due to treatment with a BTK inhibitor.
18. Have major surgery planned within 4 weeks of planned first dose of study intervention.
19. Have ongoing drug-induced liver injury, primary biliary cirrhosis, or extrahepatic obstruction caused by cholelithiasis, or cirrhosis of the liver.
20. Have significant cardiovascular disease defined as any of the following:
 - a. unstable angina or acute coronary syndrome within the past 2 months before randomization
 - b. history of myocardial infarction within 3 months before randomization
 - c. documented LVEF by any method of $\leq 40\%$ within the 12 months before randomization
Exception – individual has ≥ 2 subsequent measurements of any kind, separated by a minimum of 3 weeks, that documents LVEF recovery $>40\%$
 - d. \geq Grade 3 New York Heart Association functional classification system of heart failure, or
 - e. uncontrolled or symptomatic arrhythmias.
21. Have a QTc prolongation using Fridericia's formula (QTcF) >470 ms. See Section 8.2.3 for details and potential corrections.
22. Have hepatitis B testing results at screening indicating active infection defined as positive for HBsAg or PCR positive for HBV DNA.
Exception - Individuals with negative HBsAg and positive anti-HBc if HBV DNA is negative before randomization.
23. Have HCV defined as positive for anti-HCV antibodies.
Exception - Individuals positive for anti-HCV antibodies and negative for HCV RNA before randomization.
24. Have known active CMV infection as determined through CMV PCR testing.
25. Have known HIV infection, regardless of CD4 count.
26. Have an unstable mental health disorder.
27. Have evidence of a clinically significant uncontrolled medical condition(s) including, but not limited to, hypertension, uncontrolled systemic infection (viral, bacterial, or fungal) or other clinically significant active disease process which, in the opinion of the investigator and medical monitor, may pose a risk for participation.
Screening for chronic conditions is not required.
28. Have a clinically significant active malabsorption syndrome or other condition likely to affect gastrointestinal absorption of the oral-administered study treatments.
29. Have inflammatory bowel disease.

Previous or concomitant therapy

30. Have received prior treatment with
 - a BTK degrader, or
 - a noncovalent BTK inhibitor.
31. Have a history of allogeneic transplant.
32. Have had an autologous stem cell transplant or chimeric antigen receptor T-cell therapy within the past 90 days.
33. Require therapeutic anticoagulation with warfarin or another vitamin K antagonist.
34. Use >20-mg prednisone QD or equivalent dose of steroid per day at the time of first dose of study intervention.
35. Received a live vaccine within 28 days before randomization.
36. Require therapy with a strong CYP3A inhibitor that cannot be stopped within 14 days before the first dose of study intervention. See Section 10.8 for examples of excluded medications and suggested alternatives that are not strong CYP3A inhibitors.
37. Require therapy with a strong or moderate CYP3A4 inducer that cannot be stopped within 14 days before the first dose of study intervention. See Section 10.8 for examples of excluded medications.
38. Require therapy with substrates of P-gp and BCRP that are sensitive to minimal concentration changes. See Section 10.8 for examples of excluded medications.
39. Are currently enrolled in any other clinical study involving an investigational product or anticancer therapy except hormonal therapy. Individuals receiving investigational COVID-19 prophylaxis or treatment may be allowed in the study with sponsor approval.

Other exclusions

40. Are pregnant, or intend to become pregnant during the study, or within 30 days of last dose of study treatment or to breastfeed during the study or within 1 week of the last dose of study treatment.
41. Have a known hypersensitivity, including anaphylaxis, to any component or excipient of pirtobrutinib.
42. Are special protected populations, including those unable to sign consent for themselves.
43. Are individuals committed to an institution by virtue of an order issued with by the judicial or administrative authorities.
44. Are employees of the sponsor or site.

5.3. Lifestyle Considerations

This section is not applicable to this study.

5.4. Screen Failures

A screen failure occurs when a participant who consents to participate in the clinical study is not subsequently randomized. A minimal set of screen failure information is required to ensure transparent reporting of screen failure participants to meet the CONSORT publishing requirements and to respond to queries from regulatory authorities. Minimal information includes demography, screen failure details, and any SAE.

Individuals who do not meet the criteria for participation in this study (screen failure) may be rescreened. Each time rescreening is performed, the individual must sign a new ICF and will be assigned a new identification number.

Rescreened individuals must repeat screening procedures and tests, with the exception of imaging, if done within 42 days of planned randomization.

Repeating of laboratory tests during the screening period or repeating screening tests to comply with the protocol designated screening period does not reconstitute rescreening.

5.5. Criteria for Temporarily Delaying Enrollment of a Participant

This section is not applicable to this study. All entry criteria must be met within the specified intervals in the SoA.

See Section [10.7](#) for changes in study conduct during exceptional circumstances.

6. Study Intervention(s) and Concomitant Therapy

Study intervention is defined as any medicinal product(s) or medical device(s) intended to be administered to or used by a study participant according to the study protocol.

6.1. Study Intervention(s) Administered

This table lists the interventions used in this clinical study.

Intervention Name	Pirtobrutinib
Dosage Level(s)	CCI or 200 mg
Dose Frequency	Once daily (QD) in 28-day continuous cycles
Route of Administration	Oral
Authorized as Defined by EU Clinical Trial Regulation	Not authorized in EU

Pirtobrutinib

The participant should take pirtobrutinib at approximately the same time each day.

Pirtobrutinib may be taken with food or drink.

A vomited dose should not be redosed or replaced.

If a dose is missed by more than 12 hours, then the participant should wait and take the next dose as scheduled.

Packaging and labeling

Study interventions will be supplied by the sponsor in accordance with current Good Manufacturing Practice. Study interventions will be labeled as appropriate for country requirements.

6.2. Preparation, Handling, Storage, and Accountability

The investigator or designee must confirm appropriate storage conditions have been maintained during transit for all study intervention received and any discrepancies are reported and resolved before use of the study intervention.

Only participants enrolled in the study may receive study intervention. Only authorized study personnel may supply, prepare, or administer study intervention.

All study intervention must be stored in a secure, environmentally controlled, and monitored (manual or automated) area in accordance with the labeled storage conditions with access limited to the investigator and authorized study personnel.

The investigator or authorized study personnel are responsible for study intervention accountability, reconciliation, and record maintenance, that is, receipt, reconciliation, and final disposition records.

Further guidance and information for the final disposition of unused study interventions are provided in the study training materials.

6.3. Assignment to Study Intervention

Randomization CCI

All participants will be centrally assigned to randomized study intervention using an IWRS. Before the study is initiated, the log-in information and directions for the IWRS will be provided to each site.

Study intervention will be dispensed at the study visits summarized in SoA.

Returned study intervention should not be re-dispensed to the participants.

Participants will be randomly assigned in a CCI ratio to receive either pirtobrutinib 200 mg, CCI

Participants will be CCI CCI

6.4. Blinding

This is an open-label study.

6.5. Study Intervention Compliance

Participants must keep a daily diary to record dosing compliance of pirtobrutinib.

The site staff will assess dosing compliance at each visit by means of tablet count in returned bottles.

A record of the number of tablets dispensed to and taken by each participant must be maintained and reconciled with study intervention and compliance records. Intervention start and stop dates, including dates for intervention delays, or dose modifications, will also be recorded in the CRF and dosing diary.

Study intervention taken will be derived from the difference between the total number of tablets dispensed and returned over the course of the participant's treatment. A participant will be considered noncompliant if they are judged by the investigator to have intentionally or repeatedly taken <75% or ≥125% of the planned doses of study intervention over the course of the participant's treatment.

6.6. Dose Modification

Guidelines for making dose modifications in this study fall into these categories

- guidelines for adjusting study intervention
- guidelines for withholding study intervention
- guidelines for discontinuing study intervention
- guidelines for resuming a treatment cycle, and
- guidelines for re-escalating study intervention.

These recommendations serve as a guide and do not replace investigator judgment and applicable local recommendations if more stringent.

All dose interruptions, dose modifications, and the reasons for those changes will be recorded in the CRF.

6.6.1. Guidelines for Adjusting or Withholding or Discontinuing Study Intervention to Manage AEs

The investigator may adjust the participant’s dose or temporarily or permanently discontinue the participant from study intervention if the participant experiences a clinically significant AE as assessed by NCI CTCAE v5.0.

These principles guide investigators on when to adjust the 200-mg or CCI, or withhold, or discontinue the study intervention due to AEs.

Pirtobrutinib exhibits linear PK. The current guidance to manage AEs is to reduce the pirtobrutinib exposure level.

For participants receiving 200 mg QD, the reduction to 100 mg QD is equivalent to a 50% exposure reduction from the starting dose. A further reduction to 50 mg QD is equivalent to a 50% exposure reduction from 100 mg QD.

For participants receiving CCI QD, the reduction to CCI QD is equivalent to a CCI exposure reduction from the starting dose of CCI QD.

This table provides guidance to manage AEs.

Adverse Events	Occurrences Requiring Dose Modification	Pirtobrutinib Dose Modification Instructions		
		200 mg	CCI	

 Grade 3 or greater non-hematologic toxicity^a Absolute neutrophil count <1 to $0.5 \times 10^9/L$ with fever and/or infection Absolute neutrophil count $<0.5 \times 10^9/L$ lasting 7 or more days Platelet count <50 to $25 \times 10^9/L$ with bleeding Platelet count $<25 \times 10^9/L$ 	First occurrence	Hold pirtobrutinib until recovery to Grade 1 or baseline. May restart at original dose level. ^b		
	Second occurrence	Hold pirtobrutinib until recovery to Grade 1 or baseline. May restart at 100 mg ^c	Hold pirtobrutinib until recovery to Grade 1 or baseline. May restart at CCI ^c	Discontinue
	Third occurrence	Hold pirtobrutinib until recovery to Grade 1 or baseline. May restart at 50 mg ^c	Discontinue	
	Fourth occurrence	Discontinue		

Dose modification is not recommended for asymptomatic lymphocytosis. Asymptomatic lipase increase may not necessarily warrant dose modification.

^a Evaluate the benefit-risk before resuming treatment at the same dose for a Grade 4 non-hematological toxicity.

^b If a Grade 3 or Grade 4 treatment-related AE takes longer than 21 days to recover to Grade 1 or baseline, reduce the dose after the first occurrence.

^c If the dose was reduced previously for the same event, continue to the next lower dose level or discontinue.

The investigator should also refer to the IB for the current safety information.

Additional guidelines for withholding study intervention

If a participant needs surgery while on study intervention, the investigator should consider withholding study intervention for 3 to 7 days before and after surgery, depending on the type of surgery and risk of bleeding.

Investigators may withhold pirtobrutinib for a maximum of 28 days from the last dose to allow a participant sufficient time for recovery from treatment-related toxicity. In exceptional circumstances, a longer delay is permitted upon agreement between the investigator and the sponsor.

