2.3.3. Overall Benefit-Risk Conclusion

The safety and efficacy profile seen to date for pirtobrutinib supports the overall favorable benefit-risk for participants with CLL/SLL in this study.

3. Objectives, Endpoints, and Estimands

Objectives	Endpoints
Primary	

To compare the overall response rate of
 
 • pirtobrutinib 200 mg to CCI, and • pirtobrutinib 200 mg to CCI 	
Overall response rate, as assessed by the investigator per iwCLL 2018
 
Overall response rate is defined as the proportion of participants who achieve the best overall response at or before the initiation of subsequent anticancer therapy of
 
 • CR • CRi • nPR, or • PR
Secondary	

To determine the incidence of \geqGrade 3 AEs that occur at each pirtobrutinib dose level
	
\geqGrade 3 AEs (Section 8.3.3)

To determine the duration of response of each pirtobrutinib dose level
	
Duration of response
 
Duration of response is defined as the time from the date of the first documented CR, CRi, nPR, or PR to disease progression (per iwCLL 2018) or death from any cause

To determine the safety and tolerability of each pirtobrutinib dose level
	
Including, but not limited to
 
 • \geqGrade 3 TEAEs • SAEs • discontinuations due to an AE • dose interruptions due to an AE, and • dose reductions due to an AE
Exploratory	

To evaluate efficacy of each pirtobrutinib dose level
	
 • Progression-free survival • Overall survival 
 ○ Overall response rate and duration of response, including

Objectives	Endpoints
	partial remission with lymphocytosis
To evaluate the relationship between biomarkers and clinical outcomes	
 • Biomarkers assessed from blood samples and clinical outcomes data
To measure changes in biomarkers in response to pirtobrutinib and after progression	
 • Changes in biomarkers in response to study treatment
To further characterize the pharmacokinetics of pirtobrutinib	
 • PK parameters including, but not limited to, Cmax, Tmax, and AUC
To determine the relationship between PK and drug effects, including efficacy and safety	
 • Relationship of PK parameters to drug effects (exposure-response relationships)

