7.1. Discontinuation of Study Intervention

When necessary, a participant may be permanently discontinued from study intervention. If so, the participant will discontinue the study intervention (treatment) and will remain in the study to complete procedures for all remaining study visits, as shown in the SoA.

A participant should be permanently discontinued from study intervention if

- the participant or the participant's designee requests to discontinue study intervention
- the participant is noncompliant with study procedures or treatment
- there is disease progression determined by the investigator per iwCLL 2018 criteria. Sponsor verification of progressive disease may be requested
- the participant requires alternative treatment, unless the treatment is temporary, such as local radiation or surgery to relieve symptoms of the disease that does not otherwise meet the definition of disease progression
- there is a dose delay of more than 28 days for hematologic toxicity. In exceptional circumstances, a longer delay is permitted upon agreement between the investigator and the sponsor. See Section [10.7](#)
- the participant becomes pregnant during the study, or
- in the opinion of the investigator, the participant should permanently discontinue the study intervention for safety reasons.

If the participant, for any reason, requires treatment from another therapeutic agent that is effective for the study indication, discontinuation from study intervention will occur prior to introduction of the new agent. If medically appropriate, complete the short-term follow-up procedures before introduction of the new agent; see Section [1.3](#).

If a participant has confirmed disease progression recorded and has discontinued study intervention, the participant will be followed up for survival status until death, withdrawal of consent for survival status, or the end of the study.

See Section [6.6](#) for additional guidelines for discontinuing study intervention.

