9.3.4. Secondary Endpoints Analysis

Duration of response

Investigator-assessed DOR is defined as the time from first documented response of CR, CRi, nPR, or PR to the first documentation of disease progression (per iwCLL 2018 criteria, Section 8.1.3) or death from any cause. Following first documentation of CR, CRi, nPR, or PR, participants who are alive and without documented disease progression at the time of the data analysis cutoff date will be censored. A detailed DOR event/censoring scheme will be provided in the SAP.

Median DOR and its CCI and DOR rates and associated CCI at selected timepoints, for each treatment group will be estimated CCI CCI

Safety analysis

Safety data will be summarized for the safety population. The baseline value for the safety analysis is defined as the value collected at the time closest to and before the start of study intervention administration.

AEs will be graded by the investigator according to the NCI CTCAE v5.0 for nonhematologic and hematologic AEs. Each AE verbatim term will be coded to a System Organ Class and a Preferred Term using the MedDRA.

All TEAEs will be summarized by treatment group, including severity and relationship to study intervention.

Summaries by treatment group will be provided for the following, but not limited to

- ≥Grade 3 AESIs
- ≥Grade 3 TEAEs
- SAEs
- discontinuations due to an AE
- dose interruptions due to an AE, and
- dose reductions due to an AE.

Estimates of key safety measures will be summarized with CCI for each treatment group.

Clinical laboratory parameters will be summarized by treatment and the worst postbaseline toxicity grade that occurs during the treatment period.

Serum immunoglobulins (IgA, IgG, and IgM) will be summarized with descriptive statistics. Participants who receive IV immunoglobulin during the study will be excluded from the summary for IgG.

Additional safety endpoints, including ECOG PS, vital signs, and weight, will be summarized descriptively with further details provided in the SAP.

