9.5. Sample Size Determination

Approximately 249 participants will be randomly assigned in a CCI ratio to receive either pirtobrutinib 200 mg, CCI approximately CCI participants per dose level.

The superiority of pirtobrutinib 200 mg versus CCI as measured by investigator-assessed ORR will be tested using a CCI. With CCI participants per dose level, there is CCI power to detect a difference in ORR, assuming a CCI ORR with pirtobrutinib 200 mg and CCI ORR CCI. Efficacy boundary on the difference in ORR is approximately CCI.

CCI

The CCI ORR assumed for pirtobrutinib 200 mg is based on the results from Study 18001 for participants with CLL/SLL who were previously treated with BTK inhibitors and received pirtobrutinib at a starting dose of 200 mg. Given limited efficacy data from Study 18001 at lower dose levels, a CCI ORR was assumed for CCI since a CCI shift in true ORR (efficacy boundary of CCI is the minimal clinically meaningful difference in which the efficacy at lower doses is clearly worse than the efficacy of pirtobrutinib 200 mg.

Additionally, a sample size of CCI participants per dose level will provide approximately CCI power to detect a difference in the occurrence of Grade 3 or higher treatment-emergent AEs between any two dose levels, when the assumed incidence rates are CCI. These comparisons on treatment-emergent AEs will not be CCI CCI

10. Supporting Documentation and Operational Considerations

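### Rule-driven AE discontinuations (every pair of arms) and AE dose reductions (against the arm with no lower level) partly measure the unequal reduction ladders, not tolerability

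*Supplement*

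**What the plan says.** Section 6.6.1 of the protocol holds one table for managing AEs, with a column for each dose. The first qualifying occurrence is handled alike in all arms: hold, then possibly restart at the same dose. After that the columns differ.

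- **200 mg:** restart at 100 mg after the second occurrence. After the third: "Hold pirtobrutinib until recovery to Grade 1 or baseline. May restart at 50 mg". Stop at the fourth. The prose confirms two steps: "A further reduction to 50 mg QD is equivalent to a 50% exposure reduction from 100 mg QD".
- **One lower-dose arm:** restart at a single lower (redacted) level after the second occurrence; stop at the third.
- **The other lower-dose arm:** stop at the second occurrence. The prose describes no reduction for this arm.

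Footnote b, attached to the shared first-occurrence instruction, says that when a Grade 3 or 4 treatment-related AE recovers slowly (over 21 days), sites should "reduce the dose after the first occurrence".

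Section 3 lists "dose reductions due to an AE" among the secondary safety and tolerability endpoints, and Section 9.3.4 summarizes these and "discontinuations due to an AE" by treatment group. Section 6.6 calls the dose-modification rules a guide that leaves room for investigator judgment.

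On hold length, Section 6.6.1 says "Investigators may withhold pirtobrutinib for a maximum of 28 days from the last dose", for recovery from treatment-related toxicity generally. Section 7.1 requires permanent discontinuation when "there is a dose delay of more than 28 days for hematologic toxicity".

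**The concern.** The study rationale (Section 2.1) asks whether a lower dose improves safety without losing efficacy. Readers will look to AE-led discontinuations and reductions by arm for part of the answer. Both counts, however, depend on how many rungs each arm's ladder has as well as on how toxic the dose is.

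The two endpoints also mislead in opposite directions. A participant in the arm with no step meets the stopping rule two events sooner than one at 200 mg, so the lower dose looks worse on discontinuation. The same participant can never be recorded as dose-reduced, so the lower dose looks better on reductions. Nothing in the protocol text warns of this.

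Two wording conflicts could make sites apply the rules differently: footnote b asks for a reduction that one column does not offer, and the 28-day hold limit has a different scope in two sections.

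**Working it through.** The protocol states no expected rate, power or sample size for AE-led reductions or discontinuations, so there is no planned figure to reproduce. The ladder arithmetic in Section 6.6.1 is consistent: 100/200 = 50% and 50/100 = 50%.

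**Inputs from the table.** The arms have 2, 1 and 0 reduction steps and stop at occurrence 4, 3 and 2. The lower doses and their column headings are redacted, so I label the arms by number of steps, read from the table cells and the prose.

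**Assumptions.** The number N of qualifying occurrences per participant has the same distribution in every arm (equal toxicity). It is Poisson with mean m = 0.3, 0.5 or 1.0, and the table is followed as written.

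**Rule-driven discontinuation.** P(N ≥ k) = 1 − Σ_{i<k} e^(−m) m^i / i!, with k = 2, 3, 4 for the 0-, 1- and 2-step arms. For m = 1.0 (e^(−1) = 0.3679):

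- k = 2: 1 − 2 × 0.3679 = 26.4%
- k = 3: 1 − 2.5 × 0.3679 = 8.0%
- k = 4: 1 − 2.6667 × 0.3679 = 1.9%

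| m | 0-step | 1-step | 2-step (200 mg) |
|---|---|---|---|
| 0.3 | 3.7% | 0.4% | 0.03% |
| 0.5 | 9.0% | 1.4% | 0.2% |
| 1.0 | 26.4% | 8.0% | 1.9% |

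If the approximately 249 participants were split equally (249/3 = 83; the ratio is redacted), m = 1.0 would mean about 22, 7 and 2 stops, and m = 0.3 about 3, 0.3 and 0.

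**Overdispersion.** With a negative binomial of shape 1, P(N ≥ k) = (m/(1+m))^k. At m = 1.0 this is 0.5^2, 0.5^3 and 0.5^4, or 25.0%, 12.5% and 6.2%. The ordering is unchanged.

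**How much safer the 0-step arm would have to be.** To match the 200 mg arm's 1.9% at m = 1.0, solve 1 − (1 + x)e^(−x) = 0.019, which gives x ≈ 0.21. That is about 79% fewer qualifying events just to look equal.

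**Dose reductions.** The 200 mg and 1-step arms both first reduce at the second occurrence, so the proportion with any reduction is P(N ≥ 2) in both: 9.0% each at m = 0.5 and 26.4% each at m = 1.0. In the 0-step arm it is 0%. The mean number of reductions at m = 1.0 is 0.264 + 0.080 = 0.345 (unrounded terms) at 200 mg, 0.264 in the 1-step arm and 0 in the 0-step arm.

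**A measure the ladder does not drive.** Any first hold is P(N ≥ 1) = 1 − e^(−m): 25.9%, 39.3% and 63.2% at m = 0.3, 0.5 and 1.0, identical in all arms under equal toxicity.

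**Wording conflicts, side by side.** Footnote b calls for a reduction after a slow-recovering first event in any arm, while the 0-step column shows no lower level. The 28-day limit covers treatment-related toxicity in Section 6.6.1 but hematologic toxicity only in Section 7.1, so a prolonged hold for non-hematologic toxicity falls under one limit and not the other.

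**The case against.** The strongest reply is that the plan does not misuse these endpoints. Section 9.3.4 provides summaries by group and shows no test of reductions or discontinuations. The endpoint list is open-ended, and Section 9.3.2.5 also reports duration of therapy, dose modifications and dose intensity. This stands: the issue is interpretation, not a faulty test.

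The table is also guidance. Investigators may stop treatment for a clinically significant AE outside the ladder, and such stops dilute the contrast. Footnote c refers to the same event, so occurrences may be counted per event type, which would lower the effective mean. No event rate is visible, and at m = 0.3 the effect is a few participants. These points limit the size but do not reverse the direction.

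Three stronger readings are tempting, and the documents do not support them.

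- **That none of the tolerability endpoints can be compared.** The proportion with any reduction is comparable between 200 mg and the 1-step arm. Grade 3 or higher TEAEs, SAEs and first AE-led interruptions do not pass through the ladder.
- **That early rule-driven stopping distorts ORR.** Treatment discontinuation is handled by treatment policy (Section 3), and disease assessment continues after stopping until progression or new therapy (Section 1.3). A response after an AE-led stop still counts, and no size can be derived.
- **That the powered safety comparison is biased by time at risk.** Section 9.5 speaks of power "to detect a difference in the occurrence of Grade 3 or higher treatment-emergent AEs between any two dose levels", but the summary statistic and the status of that comparison are partly redacted. Exposure adjustment is normally left to the SAP, which is not among the documents reviewed. Any figure would rest on invented treatment durations.

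**Conclusion.** The point holds in a limited form. AE-led discontinuation is confounded with the ladder in every pair of arms, against the lower doses. AE-led reduction is confounded in any comparison with the 0-step arm, in that arm's favor. Between 200 mg and the 1-step arm only the number of reductions is affected.

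The direction follows from the table alone. The size rests on an assumed common event rate and on sites following the guidance. The gap in rule-driven stopping between the 0-step and 200 mg arms runs from about 4 percentage points at a mean of 0.3 to about 24 at a mean of 1.0 (26.4 − 1.9 = 24.5), and less if investigators depart from the table. The two wording conflicts are separate. The 28-day mismatch applies to all arms alike and adds nothing to the confounding argument.

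**What to change.** In the SAP, and briefly in Section 9.3.4:

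1. Keep the by-arm counts of AE-led discontinuations and reductions as descriptive summaries.
2. State that discontinuations (all pairs of arms) and reductions (against the arm with no lower level) partly reflect the dose-modification rule and will not be read alone as dose effects.
3. Base the between-dose tolerability comparison on measures the ladder does not drive: incidence of, and time to, the first AE meeting the table's threshold, and a composite of first AE-led hold, reduction or discontinuation. Use the first event, not the number of events, because the number of possible holds also depends on the ladder.
4. Optionally add exposure-adjusted or fixed-time incidence of Grade 3 or higher TEAEs as a supportive analysis.

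Separately, the sponsor should reconcile footnote b with the column that shows no lower level, and Section 6.6.1 with Section 7.1 on the scope of the 28-day limit. Which rule is right is a clinical matter on which this review takes no position.

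The cost is a paragraph of wording and a few extra tables. Dose changes and their reasons are already recorded in the CRF (Sections 6.5 and 6.6), and AE grades are collected. Items 1 to 4 change nothing in patient care; the reconciliation needs a protocol clarification.
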